Grade 2	Epithelial opacities; micro-cysts, micro-deposits; corneal erosion; non-central stromal opacity	Keep treatment dose level and schedule if the ophthalmological exam can be performed as needed; otherwise consider dose reduction by -1 dose level without dose schedule change at the discretion of investigator and ophthalmologist; intensive treatment with ocular lubricants enhanced with ointments; topical steroids; therapeutic contact lens may be considered at the discretion of investigator and ophthalmologist

Corneal Epitheliopathy	Definition	Management/Next Dose ^{1,2}
Grade 3	Corneal ulcer without risk of acute rupture; Central stromal opacity	1) Decrease dose to -1 dose level (or -2 dose level if event does not resolve to Grade ≤ 2 at the -1 dose level within 3 weeks) 2) Re-start at the original dose level if the first Grade 3 event resolves to Grade ≤ 2 within 3 weeks and does not recur 3) If not resolved within 3 weeks continue at reduced -1 dose level (or -2 dose level); Intensive therapy with ointments; topical steroids; therapeutic contact lens or occlusion recommended at the discretion of investigator and ophthalmologist
Grade 4	Corneal ulcer more severe than grade 3	Discontinue anetumab ravidansine; Intensive therapy with lubricants, ointments, topical steroids and antibiotics as needed; occlusion or therapeutic contact lens recommended; amniotic membrane transplant and other locally approved therapies to be considered at the discretion of investigator and ophthalmologist

 1. Other remedial therapies for corneal epitheliopathy may be added or substituted at investigator's discretion or according to the institutional standards. 2. Treatment decisions are based on corneal morphology changes only, not on visual acuity changes. 		

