7.1 Comprehensive Adverse Events and Potential Risks List (CAEPRs)

7.1.1 Comprehensive Adverse Events and Potential Risks list (CAEPR) for **Anetumab ravidansine (BAY 94-9343, NSC 791065)**

The Comprehensive Adverse Events and Potential Risks list (CAEPR) provides a single list of reported and/or potential adverse events (AE) associated with an agent using a uniform presentation of events by body system. In addition to the comprehensive list, a subset, the Specific Protocol Exceptions to Expedited Reporting (SPEER), appears in a separate column and is identified with bold and italicized text. This subset of AEs (SPEER) is a list of events that are protocol specific exceptions to expedited

reporting to NCI (except as noted below). Refer to the 'CTEP, NCI Guidelines: Adverse Event Reporting Requirements' http://ctep.cancer.gov/protocolDevelopment/electronic_applications/docs/aeguidelines.pdf for further clarification. Frequency is provided based on 652 patients. Below is the CAEPR for Anetumab ravtansine (BAY 94-9343).

NOTE: Report AEs on the SPEER **ONLY IF** they exceed the grade noted in parentheses next to the AE in the SPEER. If this CAEPR is part of a combination protocol using multiple investigational agents and has an AE listed on different SPEERs, use the lower of the grades to determine if expedited reporting is required.

Version 2.4, November 14, 2019¹

Adverse Events with Possible Relationship to Anetumab ravtansine (BAY 94-9343) (CTCAE 5.0 Term) [n= 652]			Specific Protocol Exceptions to Expedited Reporting (SPEER)
Likely (>20%)	Less Likely (<=20%)	Rare but Serious (<3%)	
BLOOD AND LYMPHATIC SYSTEM DISORDERS			
	Anemia		
EYE DISORDERS			
	Blurred vision		Blurred vision (Gr 2)
	Dry eye		Dry eye (Gr 2)
Eye disorders - Other (corneal disorder) ²			Eye disorders - Other (corneal disorder)² (Gr 2)
	Keratitis		
GASTROINTESTINAL DISORDERS			
	Abdominal pain		
	Constipation		
Diarrhea			Diarrhea (Gr 2)
	Gastroesophageal reflux disease		
Nausea			Nausea (Gr 2)
	Vomiting		Vomiting (Gr 2)
GENERAL DISORDERS AND ADMINISTRATION SITE CONDITIONS			
Fatigue			Fatigue (Gr 2)
	Fever		
INJURY, POISONING AND PROCEDURAL COMPLICATIONS			
	Infusion related reaction		
INVESTIGATIONS			
	Alanine aminotransferase increased		Alanine aminotransferase increased (Gr 2)
	Alkaline phosphatase increased		
	Aspartate aminotransferase increased		Aspartate aminotransferase increased (Gr 2)

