- a: Physical exam at pre-study includes height/weight, vital signs, demographics and medical history. Physical exam at all other visits includes weight and vital signs. Vital signs include pulse, blood pressure and temperature.
- b: For all patients at screening then only those randomized to receive anetumab ravidansine: Perform ophthalmologic exam within 28 days prior to Cycle 1 Day 1. The exam will include visual acuity [BCVA according to ETDRS, or Snellen, or Landolt C or other charts], intra-ocular pressure, dry eye test [Schirmer test] and slit lamp. For all subsequent cycles after Cycle 1, visual acuity and a slit lamp examination will be repeated before infusion in every cycle and at safety follow-up visit, or more frequently at investigator's and ophthalmologist's discretion. The IOP measurement is to be repeated during anetumab ravidansine therapy if the

patient receives steroid eye drops for more than 10 days as treatment for corneal epitheliopathy. This measurement is performed at 2 weeks and 6 weeks after the initiation of steroid treatment. If IOP increases by < 7 mmHg, the frequency of IOP evaluation can be reduced to every 4 months. If IOP increases by ≥ 7 mmHg, a medical management plan with follow-up IOP evaluations will be initiated after consultation with an ophthalmologist and investigator. The Schirmer test is performed at baseline and then at C3D1 and C5D1. All these tests may be repeated during treatment at the investigator's discretion.

Note: Ophthalmologic exams do not need to be continued for patients assigned to combination therapy who later discontinue anetumab ravidansine due to non-ocular toxicities.

- c: Labs include albumin, alkaline phosphatase, total bilirubin, bicarbonate, BUN, calcium, chloride, creatinine, glucose, LDH, phosphorus, potassium, total protein, SGOT [AST], SGPT [ALT], sodium.
- d: Patients receiving pembrolizumab should be monitored for changes in thyroid function at the timepoints listed in the calendar and as clinically indicated for clinical signs and symptoms of thyroid disorders.
- e: Serum pregnancy test for females of childbearing potential.
- f: Echocardiogram or Multigated Acquisition Scan (MUGA; radionuclide angiography) is performed at pre-study and then only as clinically indicated.

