13.5.4 Adverse Events

All eligible patients that have initiated treatment will be considered evaluable for assessing adverse event rate(s). The maximum grade for each type of adverse event will be recorded for each patient, and frequency tables will be reviewed for each arm to determine patterns. Additionally, the relationship of the adverse event(s) to the study treatment will be taken into consideration. The overall adverse event rates for Grade 3 or higher hematologic and non-hematologic adverse events at least possibly related to treatment will be compared between the two treatment groups using the Chi-square test (or Fisher's exact test if the data in the contingency table is sparse).

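### Eye exams are scheduled after screening only in the combination arm, yet the by-arm adverse-event tables and the pooled grade 3+ test make no allowance for the unequal detection of eye events.

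*Combined protocol and SAP*

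**What the plan says.** Section 10, footnote b, gives the eye-exam schedule as "For all patients at screening then only those randomized to receive anetumab ravidansine". For Group 2 it continues: "For all subsequent cycles after Cycle 1, visual acuity and a slit lamp examination will be repeated before infusion in every cycle". Visual acuity and slit lamp are also due at the safety follow-up visit, and the Schirmer test at C3D1 and C5D1. Two qualifications follow. Unscheduled exams are possible: "All these tests may be repeated during treatment at the investigator's discretion". Exams can also lapse within Group 2: "Ophthalmologic exams do not need to be continued for patients assigned to combination therapy who later discontinue anetumab ravidansine due to non-ocular toxicities".

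Section 13.5.4 records the maximum grade of each type of adverse event per patient and reviews frequency tables by arm. It then plans one between-arm comparison: "The overall adverse event rates for Grade 3 or higher hematologic and non-hematologic adverse events at least possibly related to treatment will be compared", by chi-square or Fisher's exact test. No significance level is given. Eye events are neither set apart nor excluded, and the exam schedule is not mentioned.

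The anetumab ravtansine list in Section 7.1.1 places "Eye disorders - Other (corneal disorder") in the likely (>20%) column. A footnote to that list includes microcysts, deposits and verticillata in the term. The corneal table in Section 6.2 grades by appearance: any stage of superficial punctate keratitis is grade 1, micro-cysts and micro-deposits are grade 2, and central stromal opacity is grade 3. Its note adds: "Treatment decisions are based on corneal morphology changes only, not on visual acuity changes". The pembrolizumab list in Section 7.1.2 has uveitis and Vogt-Koyanagi-Harada syndrome as rare but serious (<3%).

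**The concern.** Several of the eye findings at issue are seen at the slit lamp and need not cause any complaint. In Group 2 they are looked for before every infusion from Cycle 2. In Group 1 they come to light only if the patient has symptoms or the investigator chooses to examine. The eye rows of the by-arm tables therefore compare a searched arm with an unsearched one, and the difference is the sum of what the drug does and what the extra looking finds. Nothing in Section 13.5.4 would let a reader separate the two.

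Eye events are non-hematologic, so they also enter the pooled grade 3+ test. That is the plan's only formal between-arm harm comparison, and what anetumab ravtansine adds to the toxicity of pembrolizumab is the safety question that the randomized part can answer. A difference in ascertainment there deserves at least a sensitivity analysis.

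**Working it through.** **Arm size.** Section 13.1.3.3 gives 49 per arm for 20% versus 40%, one-sided 0.10, 80% power. The fixed-design two-proportion formula gives 47 per arm, and power at 49 is 0.816. Simulation with the futility look gives 0.817 against the stated 0.805. The stated size reproduces closely, and 49 per arm is used below.

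**Any-grade eye rows.** Expected count = 49 × true rate × share detected. The true rate (20% in both arms) and the Group 1 detection shares are assumptions chosen to show the mechanism. The documents give no such rate for Group 1.

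- Group 2, all detected: 49 × 0.20 = 9.8.
- Group 1, half detected: 49 × 0.20 × 0.50 = 4.9.
- Group 1, a quarter detected: 49 × 0.20 × 0.25 = 2.45, about 2.5.

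The true rates are equal here, so the whole gap is detection. The plan only tabulates these rows. If a chi-square test were applied to this row (two-sided 0.05), it would reject 30% or 67% of the time, against 5% with equal detection.

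**Pooled grade 3+ test.** Let p be the rate of grade 3+ related events other than eye events, the same in both arms. Let q be the rate of grade 3+ eye events that Group 2 records and Group 1 misses entirely. The recorded rates are p in Group 1 and p + (1 − p)q in Group 2. The test is z = (difference in observed proportions) / √[p̄(1 − p̄) × 2/49], where p̄ is the pooled proportion, rejecting at |z| > 1.96. Two-sided 0.05 is assumed. Exact binomial enumeration gives these rejection probabilities:

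| q | p = 10% | p = 15% | p = 20% | p = 30% |
|---|---|---|---|---|
| 0 | 5.9% | 5.5% | 5.2% | 4.9% |
| 1% | 6.1% | 5.7% | 5.3% | 5.0% |
| 2% | 6.8% | 6.1% | 5.6% | 5.1% |
| 3% | 7.9% | 6.9% | 6.1% | 5.4% |

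The largest rise is 7.9 − 5.9 = 2.0 points, at q = 3% and p = 10%.

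**Why 3% is a sensible upper value for q.** Detection bias needs events that also occur in Group 1 and go unseen there. The eye terms that pembrolizumab's list links to the drug, uveitis and Vogt-Koyanagi-Harada syndrome, are both in the <3% column. For uveitis that means fewer than 0.03 × 49 = 1.5 Group 1 patients at any grade, and fewer still at grade 3+ without symptoms. Corneal disorder, keratitis and dry eye are on the anetumab ravtansine list only. Background eye disease could add events, but the documents give no rate for it.

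**Which findings can reach the test.** In the Section 6.2 table, punctate keratitis, micro-deposits and non-central opacity are grade 1 or 2, so they cannot enter a grade 3+ test. Central stromal opacity is grade 3 and could be found only at an exam. Section 7.2 specifies CTCAE version 5.0 for adverse-event reporting, and no passage says that the morphological grades feed the adverse-event tables.

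**The case against.** The strongest reply is that monitoring the arm exposed to the eye toxin is reasonable and that the excess it finds will be largely real, since corneal disorder is listed at >20% for anetumab ravtansine. That stands, and no change to the exam schedule is suggested.

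A reader might go further and infer that eye events found at exams could drive the pooled test. With a further 5%, 10% or 15% of Group 2 having grade 3+ eye events and p between 10% and 30%, the chance of p<0.05 is 6–11%, 11–26% and 19–45%. The arithmetic is right, but it gives Group 1 a true eye rate of zero. For events caused by anetumab ravtansine those figures are power to detect a real harm, not error, and the documents give no grade 3+ eye rate to support them.

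It is also fair to say that the consequence is limited. Section 13.5.4 sets no significance level and no decision rule, the phase 2 conclusion rests on response, and eye events already have rows of their own. Adverse events are evaluated throughout in both arms, so symptomatic eye events in Group 1 are captured. The point that survives is narrower: the eye rows carry no warning that only one arm was routinely examined, and the pooled test is not shown without them.

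**Conclusion.** The concern holds for the by-arm eye rows and only weakly for the pooled grade 3+ test. In the rows, the size of the between-arm difference cannot be read as drug effect. The illustration (9.8 against 4.9 or 2.5) shows how large a gap detection alone could produce, but it rests on an assumed common rate of 20% and assumed detection of a half or a quarter. In the pooled test the distortion is at most about 2 points if undetected Group 1 grade 3+ eye events are 3% or less, under an assumed two-sided 0.05 test.

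The documents do not support reading a Group 2 eye excess as mainly an artefact, because corneal toxicity is an expected effect of the drug. Nor do they support saying that Group 1 eyes go unexamined: no exam is scheduled, but discretionary ones are allowed. Detection also varies within Group 2, since exams may stop once anetumab ravtansine is discontinued for non-ocular toxicity. This is a worthwhile correction to a secondary safety analysis and does not touch the primary endpoint.

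**What to change.** In Section 13.5.4:

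- Keep the planned all-event grade 3+ test as the overall harm comparison, and add the same test with Eye Disorders excluded as a sensitivity analysis. The second test should not be described as fully equal in ascertainment, because the remaining terms still depend on investigator attribution.
- Report eye events in a separate by-arm table that states the exam schedule of each arm. Describe findings made only at scheduled exams as Group 2 incidence, not as a between-arm difference.
- Where feasible, flag eye events on the adverse-event form as symptomatic or exam-only.
- Use the PRO-CTCAE blurred-vision item as supportive data only. It has the same schedule in both arms, but it is optional for sites and patients and covers only cycles 1–3 (weekly) and the off-study visit.

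The cost is a few lines of analysis text, one further test, one table and, if adopted, one form field. No eye exams are added. The downsides are small: one more harm comparison is reported, and the symptomatic flag may itself be recorded more readily in Group 2, whose patients have an eye exam each cycle. If the flag is impractical, the two tests and the stated schedule need no new data.

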11. MEASUREMENT OF EFFECT

11.1 Antitumor Effect – Solid Tumors

Response and progression will be evaluated in this study using modified pleural RECIST for pleural disease (27) and the international criteria proposed by the revised Response Evaluation Criteria in Solid Tumors (RECIST) guideline (version 1.1) for non-pleural disease (68). Changes in the largest diameter (unidimensional measurement) of the tumor lesions and the shortest diameter in the case of malignant lymph nodes are used in the RECIST criteria.

11.1.1 Schedule of Evaluations

For the purposes of this study, patients should be re-evaluated for response every 9 weeks. In addition to a baseline scan, confirmatory scans should also be obtained 4-6 weeks following initial documentation of objective response.

11.1.2 Definitions

11.1.2.1 Evaluable for Toxicity

All patients will be evaluable for toxicity from the time of their first treatment with anetumab ravidansine and pembrolizumab or pembrolizumab.

11.1.2.2 Evaluable for Objective Response

All patients meeting the eligibility criteria who have signed a consent form, have been randomized and have begun treatment will be evaluable for response. These patients will have their response classified according to the definitions stated below

11.1.3 Disease Parameters

11.1.3.1 Pleural Measurable Disease

At baseline, the pleural disease to be measured should have a short-axis diameter of at least 1 cm for at minimum one of the 6 measurements, as lesions < 1 cm are considered non-measurable. Unidimensional measurements of tumor thickness perpendicular to the chest wall or mediastinum should be performed, measured in 2 sites (or positions) at 3 separate levels on transverse cuts of contrast-enhanced CT scan (or MRI). The sum of the measurements which meet the definition of measurable disease defines a pleural unidimensional measure: sum of up to 6 pleural thickness measurements = 1 univariate diameter. Transverse cuts used for measurements must be at least 1 cm apart and related to anatomical landmarks in the thorax as determined by the reviewer during baseline assessment by means of appropriate markers these cuts are chosen to allow reproducible assessment at later time points. If measurable tumor is present, transverse cuts in the upper thorax, above the level of division of the main bronchi are

preferred. At reassessment, pleural thickness must be measured at the same position at the same level and by the same observer, whenever possible. This is not necessarily the greatest tumor thickness at that level.

Tumor lesions that are situated in a previously irradiated area might or might not be considered measurable. If there is demonstrable progression following radiation, then a previously irradiated lesion may be included as measurable.

11.1.3.2 Extra-Pleural Measurable Disease

Measurable lesions are defined as those that can be accurately measured in at least one dimension (longest diameter to be recorded) as ≥ 20 mm (≥ 2 cm) by chest x-ray or as ≥ 10 mm (≥ 1 cm) with CT scan, MRI, or calipers by clinical exam. All tumor measurements must be recorded in millimeters (or decimal fractions of centimeters).

11.1.3.3 Malignant Lymph Nodes

To be considered pathologically enlarged and measurable, a lymph node must be ≥ 15 mm (≥ 1.5 cm) in short axis when assessed by CT scan (CT scan slice thickness recommended to be no greater than 5 mm [0.5 cm]). At baseline and in follow-up, only the short axis will be measured and followed.

11.1.3.4 Non-Measurable Disease

All other lesions (or sites of disease), including small lesions (longest diameter < 10 mm [< 1 cm] or pathological lymph nodes with ≥ 10 to < 15 mm [≥ 1 to < 1.5 cm] short axis), are considered non-measurable disease. Bone lesions, leptomeningeal disease, ascites, pleural/pericardial effusions, lymphangitis cutis/pulmonitis, inflammatory breast disease, and abdominal masses (not followed by CT or MRI), are considered as non-measurable.

Note: Cystic lesions that meet the criteria for radiographically defined simple cysts should not be considered as malignant lesions (neither measurable nor non-measurable) since they are, by definition, simple cysts.

‘Cystic lesions’ thought to represent cystic metastases can be considered as measurable lesions, if they meet the definition of measurability described above. However, if non-cystic lesions are present in the same patient, these are preferred for selection as target lesions.

11.1.3.5 Target Lesions

All measurable lesions including the sum of the pleural thickness measurements and up to a maximum of 2 lesions per organ and 5 lesions in total, representative of all involved organs, should be identified as **target lesions** and recorded and measured at baseline. Target lesions should be selected on the basis of their size (lesions with the longest diameter), be representative

of all involved organs, but in addition should be those that lend themselves to reproducible repeated measurements. It may be the case that, on occasion, the largest lesion does not lend itself to reproducible measurement in which circumstance the next largest lesion which can be measured reproducibly should be selected. A sum of the diameters (longest for non-nodal lesions, short axis for nodal lesions) for all target lesions will be calculated and reported as the baseline sum diameters. If lymph nodes are to be included in the sum, then only the short axis is added into the sum. The baseline sum diameters will be used as reference to further characterize any objective tumor regression in the measurable dimension of the disease.

11.1.3.6 Non-Target Lesions

Any other lesions (or sites of disease) beyond the target lesions should be identified as **non-target lesions** and should also be recorded at baseline. Measurements of these lesions are not required, but the presence, absence, or in rare cases unequivocal progression of each should be noted throughout follow-up.

11.1.4 Methods for Evaluation of Measurable Disease

All measurements should be taken and recorded in metric notation using a ruler or calipers. All baseline evaluations should be performed as closely as possible to the beginning of treatment and never more than 4 weeks before the beginning of the treatment.

The same method of assessment and the same technique should be used to characterize each identified and reported lesion at baseline and during follow-up. Imaging-based evaluation is preferred to evaluation by clinical examination unless the lesion(s) being followed cannot be imaged but are assessable by clinical exam.

11.1.4.1 Clinical Lesions

Clinical lesions will only be considered measurable when they are superficial (*e.g.*, skin nodules and palpable lymph nodes) and ≥ 10 mm (≥ 1 cm) diameter as assessed using calipers (*e.g.*, skin nodules). In the case of skin lesions, documentation by color photography, including a ruler to estimate the size of the lesion, is recommended.

11.1.4.2 Chest x-ray

Lesions on chest x-ray are acceptable as measurable lesions when they are clearly defined and surrounded by aerated lung. However, CT is preferable.

11.1.4.3 Conventional CT and MRI

This guideline has defined measurability of lesions on CT scan based on the assumption that CT slice thickness is 5 mm (0.5 cm) or less. If CT scans have slice thickness greater than 5 mm (0.5 cm), the minimum size for a measurable lesion should be twice the slice thickness. MRI is also acceptable in certain situations (*e.g.* for body scans).

Use of MRI remains a complex issue. MRI has excellent contrast, spatial, and temporal resolution; however, there are many image acquisition variables involved in MRI, which greatly impact image quality, lesion conspicuity, and measurement. Furthermore, the availability of MRI is variable globally. As with CT, if an MRI is performed, the technical specifications of the scanning sequences used should be optimized for the evaluation of the type and site of disease. Furthermore, as with CT, the modality used at follow-up should be the same as was used at baseline and the lesions should be measured/assessed on the same pulse sequence. It is beyond the scope of the RECIST guidelines to prescribe specific MRI pulse sequence parameters for all scanners, body parts, and diseases. Ideally, the same type of scanner should be used and the image acquisition protocol should be followed as closely as possible to prior scans. Body scans should be performed with breath-hold scanning techniques, if possible.

